10.2 Source Documents

The primary source document for this study will be the subject's medical record. If the Investigators maintain separate research records, both the medical record and the research records will be considered the source documents for the purposes of auditing the study. The

investigator will retain the source documents. The Investigator will permit monitoring and auditing of this data, and will allow NIAID, IRB/IEC, and regulatory authorities access to the original source documents, regardless of media.

The Investigator is responsible for assuring that the data collected is complete, accurate, and recorded in a timely manner. Source documentation (the point of initial recording of information) should support the data collected on the eCRF. All eCRFs should be reviewed by the Investigator and signed as required with written or electronic signature, as appropriate. Data for eCRFs will be collected directly from subjects, clinical assessments, and tests during study visits or will be abstracted from subjects' medical records. The subject's medical record must record his/her participation in the clinical trial, including obtaining informed consent, concomitant medications (with doses and frequency), medical interventions or treatments that were administered, and adverse reactions experienced during the trial.

10.3 Data Management Plan

Study data will be collected at the study site(s) and maintained on eCRFs. These forms are to be completed on an ongoing basis during the study. Corrections on any study related source record must be made by striking through the incorrect entry with a single line (taking care not to obliterate or render the original entry illegible) and entering the correct information adjacent to the incorrect entry. Corrections to paper sources must be initialed and dated by the person making the correction.

10.4 Data Capture Methods

Clinical data will be entered into an Internet Data Entry System (IDES) (US 21 CFR 11-compliant). The data system includes password protection and internal quality checks, to identify data that appear inconsistent, incomplete, or inaccurate.

10.5 Study Record Retention

The Investigator is responsible for retaining all essential documents listed in the ICH Good Clinical Practice Guideline. The US FDA requires study records to be retained for up to 2 years after marketing approval or disapproval (21 CFR 312.62), or until at least 2 years have elapsed since the formal discontinuation of clinical development of the investigational agent for a specific indication. These records are also to be maintained in compliance with IRB/EC, state, and federal medical records retention requirements, whichever is longest.

All stored records are to be kept confidential to the extent provided by federal, state, and local law. It is the Investigator's responsibility to retain copies of source documents until receipt of written notification to the contrary from OCRPRO/NIAID. No study document should be destroyed without prior written agreement between OCRPRO /NIAID and the Principal Investigator. Should the Investigator wish to assign the study records to another party and/or move them to another location, the Investigator must provide written notification of such intent to OCRPRO /NIAID with the name of the person who will accept responsibility for the transferred records and/or their new location.

NIAID must be notified in writing and written NIAID permission must be received by the site prior to destruction or relocation of research records.

11 HUMAN SUBJECTS

11.1 IRB/IEC Approval

This protocol, informed consent document, diary card, relevant supporting information, and all types of patient recruitment or advertisement information must be submitted to the IRB/IEC for review and must be approved before the study is initiated.

Any amendments must also be approved by the IRB/IEC prior to implementing changes in the study.

The Investigator is responsible for keeping the IRB/IEC apprised of the progress of the study as deemed appropriate, but in any case at least once a year. The Investigator must also keep the IRB/IEC informed of any significant AEs.

11.2 Compliance with Good Clinical Practices (GCP)

This study will be conducted in compliance with the conditions stipulated by NIAID and local IRB/IEC, informed consent regulations, US FDA and local regulatory agencies, and supported by ICH/GCP guidelines. In addition, all local regulatory requirements will be adhered to, in particular those which afford greater protection to the safety of the trial subjects.

11.3 Informed Consent Process

Informed consent is a process where information is presented to enable persons to voluntarily decide whether or not to participate as a research subject. It is an on-going conversation between the human research subject and the researchers about the essential information about the study, which begins before consent is given and continues until the end of the subject's involvement in the research. Discussions of essential information about the research will include the study's purpose, duration, experimental procedures, alternatives, risks, and benefits, and subjects will have the opportunity to ask questions and have them answered.

The participants will sign the informed consent document prior to any procedures being done specifically for the study. The participants may withdraw consent at any time throughout the course of the trial. A copy of the informed consent document will be given to the participants for their records. The researcher will document the signing of the consent form in the subject's medical record. The rights and welfare of the participants will be protected by emphasizing to them that the quality of their medical care will not be adversely affected if they decline to participate in this study.

Children will receive an assent according to their institutional and or IRB/EC requirements.

11.4 Anonymity and Confidentiality

The information obtained during the conduct of this clinical study is confidential. The results of the research study may be published, but patient names or identities will not be revealed. Records will remain confidential. To maintain confidentiality, the investigators at each site will keep records in locked cabinets and the results of tests will be coded to prevent association with the subject's names.

11.5 Compensation

Each site is responsible for generating a compensation scheme as applicable (accounting for travel cost and time lost from work for outpatient visits), and that fits the local legal and regulatory requirements as well as the cultural norm. Any compensation must be reviewed by the local IRB/IEC.

12 STORED SPECIMENS, AND DATA

12.1 Samples/Specimens

The samples collected during this study are for clinical laboratory and virologic (respifinder) testing only. No samples are stored as part of this protocol.

12.2 Storage of Data

Data will be stored using codes assigned by the sponsor. Data will be kept in password-protected computers, which are located in locked rooms.

12.3 Storage of Genetic Sample

No samples are being stored for genetic testing on the subjects.

12.4 Reporting Loss or Destruction of Samples/Specimens/Data

Any loss or unanticipated destruction of data (for example, misplacing a printout of data with identifiers) will be reported to the corresponding IRB/IECs.

Any inadvertent release or unanticipated destruction of centrally maintained data will be reported to all IRB/IECs.

### **Introduction**

This document describes the content proposed for the primary statistical analysis of NTZ-SARI. The focus is on analyses that address the major randomized comparisons for key safety, tolerability and efficacy outcome measures, including those needed to address the study's primary objective as well as secondary objectives.

## Study Background and Objectives

Respiratory viruses are a significant cause of hospitalization for respiratory tract infections. Etiologic agents include influenza, parainfluenza virus, rhinovirus, adenovirus, metapneumovirus, respiratory syncytial virus (RSV), bocavirus and coronavirus. Of these, only influenza has a licensed treatment. Nitazoxanide (NTZ) is a licensed anti-infective agent with activity against many of these respiratory viruses. In a pediatric Phase 2 study of outpatient ILI, the NTZ cohort showed symptom resolution in 4 days versus 7 days in the placebo group. In a 624 person Phase 3 study of ILI, the NTZ cohort showed symptom resolution in 94 h compared to 108 h in the placebo group ( $p=0.0026$ ). These benefits were observed in the entire cohort, not just those infected with influenza. If similar efficacy can be seen in the inpatient ILI population, there could be reductions in duration of hospitalization, morbidity, and costs.

The study is a multicenter, randomized, double-blind, placebo controlled trial to evaluate the efficacy of NTZ + standard of care (SOC) compared to placebo (PCB) + SOC in treating acute severe viral respiratory infections in adults and children  $\geq 12$  months old with SARI. It is anticipated that SOC would likely include antibiotics and may include treatment for influenza. The study is designed to enroll a total of 290 subjects who will be randomized in a 1:1 ratio. Subjects will be followed on Days 3, 7, 14, and 28. The subject will be discharged from the hospital when clinically indicated as determined by the treating physician – follow-up visits may occur as inpatients or as outpatients. Subjects still hospitalized on Day 28 will be followed until discharged from the hospital.

## Study Objectives

**Primary Objective:** Evaluate the effect of NTZ in addition to SOC as compared to PCB + SOC in the treatment of SARI as measured by the time to hospital discharge

### Secondary Objectives:

1. Evaluate the clinical efficacy of NTZ + SOC vs. PCB + SOC with regards to:
  - Percent hospitalized at Study Day 3, 7, 14 and 28
  - Death by Study Day 28
  - Duration of clinical symptoms (defined in Section 7.3.1.2)
  - Duration of fever
  - Use of supplemental oxygen (or increase greater than baseline oxygen requirement)
  - Admission to ICU
  - Intubation/mechanical ventilation
  - Proportion of subjects who develop complications including pneumonia, respiratory failure requiring mechanical ventilation, acute respiratory distress syndrome (ARDS), sepsis, or bronchiolitis.
  - Time to resumption of normal activity
  - Antibiotic/antiviral use during hospitalization
  - Systemic corticosteroid use during hospitalization
  - Re-hospitalization within 28 days
2. Evaluate the virologic efficacy of NTZ + SOC vs. PCB + SOC with regards to:
  - Percent cessation of viral shedding at Study Day 3

3. Evaluate the safety and tolerability of NTZ assessed by:
  - Cumulative incidence and severity of adverse events (AEs)
  - Cumulative incidence of serious AEs (SAEs)
  - Cumulative incidence of laboratory abnormalities on Study Days 3, 7 and 28

## Study Endpoints:

### Primary Endpoint:

- Duration of hospitalization (days and hours)

### Secondary Endpoints:

#### Clinical Endpoints:

- Hospitalization on Study Days 3, 7, 14, and 28
- Date and time of hospital discharge
- Date of death, if applicable
- Clinical symptoms (measured daily through Study Day 14 and then again on Study Day 28)
- Temperature (measured daily through Study Day 14 and then again on Study Day 28)
- Oxygen use
- Date of admission to ICU and discharge from ICU, if applicable
- Date of intubation/extubation, if applicable
- Presence of complications during study (pneumonia, respiratory failure requiring mechanical ventilation, ARDS, sepsis, or bronchiolitis)
- Global assessment (measured daily through Study Day 14 and then again on Study Day 28) (defined in Section 7.3.1.3)
- Antibiotic/antiviral use during hospitalization (number and duration)
- Re-hospitalization within 28 days
- Use of systemic corticosteroids

#### Virologic Endpoints:

- Presence of virus on nasopharyngeal (NP) swab (or aspirate) at Study Day 3 (same virus as Day 0)

#### Safety Endpoints:

- AEs
- SAEs
- Chemistry and hematologic laboratory assessments on Study Days 3, 7 and 28

## Analysis Plan

### Subject Populations

Here we give the definitions for the populations that will be referred to for different analyses.

- Enrolled: all subjects that signed consent
- Intention to Treat (ITT) population: per protocol defined as all participants who are randomized and received at least 1 dose of the study drug, and for analysis the treatment group will be assigned as randomized.
- ITT age subgroups (only on specified analyses):
  - Adults  $\geq$  18 years
  - Children aged  $<18$  years
- ITT pediatric formulation subgroups (only on specified analyses; may be omitted depending on the number of subjects enrolled in each pediatric subgroup):
  - Children  $\geq$  13 years and  $<18$  years (children that take the adult tablet formulation)
  - Children aged  $<13$  years (as this is the age for pediatric formulation)
- ITT virology subgroups (only on specified analyses):
  - Influenza A or B
    - Influenza A
    - Influenza B
  - RSV
  - Human Metapneumovirus
  - Rhinovirus/Enterovirus
  - Adenovirus
  - Mycoplasma pneumoniae
  - Chlamydophila pneumoniae
  - Legionella pneumophila
  - Bordetella pertussis
  - Parainfluenza
  - Bocavirus
  - Coronavirus

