5.1 Blinding, Randomization, Stratification, and Treatment Assignment

Treatment kits will be blinded and numbered. The two treatment arms are not distinguishable at the site. Therefore the study team, the pharmacy, and the monitors will be blinded.

The randomization scheme will be prepared by the sponsor. Those unblinded are limited to the statistician not involved with the study who generated the randomization code, and the pharmaceutical group that packaged the study drug. The Data and Safety Monitoring Board (DSMB) will have access to the unblinding code in a sealed envelope.

The study will remain blinded until after the last subject enrolled has completed the last follow-up visit and all data queries have been resolved. The study will then be unblinded for analysis.

Randomization will be built into the treatment kit order at each site (i.e., kit #101 may be NTZ or PCB depending on the randomization scheme).

Randomization will be stratified by sites and by adult and pediatric (<12 years). Randomization will occur in blocks of 4. Each site will receive study drug in multiples of 4, thus ensuring randomization is balanced by site.

Subjects who meet all criteria for enrollment will be assigned the next study kit at a site. Kits will be assigned in a consecutive manner starting with the first kit number in the block at each site.

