5.2 Study Regimens and Administration

The sponsor will supply each site with study agent near the time of site activation. Each randomized subject will receive a study drug kit consisting of 5 days of treatment. The site pharmacy will distribute the study kits. The method of supplying study agent to hospitalized subjects will be customized at each site.

Subjects take the medication twice daily, with food, and each dose will consist of the following:

Adults and Children 12 years and older:

The active formulation for this study is a yellow, film-coated tablet that contains 300 mg NTZ plus standard excipients. This is an extended release formulation of licensed NTZ. This formula provides a mean AUC_t 29 $\mu\text{g}^*\text{hr}/\text{mL}$ and mean C_{\min} (12 h) 0.8 $\mu\text{g}/\text{mL}$.

The placebo tablet will have the same appearance and inactive ingredients as the active tablet.

Group 1 (NTZ): 2 NT-300 mg tablets orally BID x 5 days.

Group 2 (Placebo): 2 placebo tablets orally BID x 5 days.

Children younger than 12 years:

The formulation for children younger than 12 years is the currently licensed suspension of nitazoxanide (Alinia®), or matching placebo.

Group 1 (NTZ):

4-11 years: 10 mL oral suspension (200 mg NTZ) every 12 hours x 5 days

1-3 years: 5 mL oral suspension (100 mg NTZ) every 12 hours x 5 days

Group 2 (Placebo):

4-11 years: 10 mL oral suspension (placebo) every 12 hours x 5 days

1-3 years: 5 mL oral suspension (placebo) every 12 hours x 5 days

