1.50 Days	1.83	.66	1.52	.78	80%	174
1.50 Days			1.52	.78	90%	232
1.25 Days	1.83	.66	1.58	.76	80%	258
1.25 Days			1.58	.76	90%	344
1.00 Day	1.83	.66	1.64	.74	80%	430
1.00 Day			1.64	.74	90%	576

^a Delta is the assumed reduction in the mean number of days in the hospital under treatment compared to placebo.

^b N is the total sample size.

We see that with about 258 patients total the study is 80% powered to detect a 1.25 day improvement in the time to hospital discharge. This difference is similar to our assumptions. To allow for up to 10% dropouts we will recruit 290 patients. If the difference was 1.5 days, the study would have 90% power to detect the difference in the treatment arms.

While a 1.25 day improvement is clinically meaningful and easily interpretable for a population with a mean hospital stay of 7.7 days, it is also a reasonable estimate of the effect of NTZ we might see. The NTZ IB describes a Phase 2b-3 study in adults and adolescents with acute uncomplicated ILI. In all subjects, the mean time to resolution of symptoms was 95 hours in the NTZ group compared to 108 hours in the placebo group, thus there is about a 12% reduction in the time to resolution (12% = (108 hr - 95 hr)/108 hr x 100%). Our hoped for treatment effect of a 1.25 day reduction in hospital duration is a 16% reduction in the time to hospital discharge (16% = (1 day/7.7 day x 100%)).

Kaplan Meier curves of time to hospitalization discharge over 28 days will be used to compare the 2 groups. In these curves, deaths will be counted as being in the hospital at day 28. The between group difference in median time to discharge will be used to estimate the treatment effect and will be reported along with a 95% two-sided confidence interval.

Important additional analyses will be to repeat the primary analysis for those who are influenza positive. Other subgroups include age (<12 years of age, \geq 12 years of age) and pathogen type.

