### 3. Selected characteristics of participants at baseline (Day 0) (ITT)

Baseline is defined as the last observation prior to study drug administration. P-values using the test of means for continuous variables, test of proportions for binary endpoints or chi-square tests for categorical endpoints

- Demographics [14.1.3]
  - Table: Age (median, 25th and 75th percentile, mean, min, max)
  - Table: number randomized by age group (<2 years, ≥2 years to <8 years, ≥8 years to <13 years, ≥13 years to <18 year, ≥18 years to <65 years, ≥65 years).
  - Sex (%)
  - Self-reported NIH race/ethnicity (%)
  - Medical History (occurring in 5% or more of the study population)
  - BMI for adults age ≥18 years
  - Z score for age <18 years
  - Smoking History
- Baseline Disease Characteristics [14.1.4.1, 14.1.4.2, 14.1.4.3, 14.1.4.4]
  - Influenza vaccination history (categorical - vaccinated the season of enrollment)
  - Confirmed pathogen by multiplex PCR (i.e. Respifinder®). Include totals for pathogen type (e.g. all influenzas), and for each strain (e.g., H1N1 influenza)
  - Days since onset of symptoms (onset of symptoms to randomization).
  - Days since onset of symptoms to first dose.
  - SaO2

- Severity of illness score
  - Sequential Organ Failure Assessment (SOFA) score for subjects  $\geq$  24 months of age
  - Tal bronchiolitis score for subjects  $<$  24 months of age
- Charlson comorbidity index.
- Chronic oxygen use
- Oxygen requirement (yes/no)
- ICU requirement (yes/no)
- Presence of Complications
  - Pneumonia (clinical diagnosis supported by radiographic data)
  - Respiratory failure requiring mechanical ventilation (documentation of mechanical ventilation)
  - ARDS (clinical diagnosis supported by radiographic data)
  - Sepsis (clinical diagnosis)
  - Bronchiolitis (clinical diagnosis)
- Presence of symptoms for each of the following (defined as 2 or 3 = symptoms present):
  - Cough
  - Sore throat
  - Fatigue
  - Headache
  - Myalgia
  - Rhinorrhea
  - Nausea
  - Vomiting
  - Diarrhea
- CBC with differential white cell count (to include neutrophil, lymphocyte, and eosinophil percentages), hemoglobin, hematocrit, and platelets
- Blood chemistries (creatinine, ALT/GPT, AST/GOT, total bilirubin, LDH, CRP)
- Global Assessment
  - Adult
    - Overall question
    - Function question
  - Pediatric
    - Activity
    - Diet

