## 11. Primary Endpoint (ITT, ITT age subgroups, ITT pediatric formulation subgroups, ITT virology subgroups)

Table to show the completeness of the primary endpoint should include number (%) with [14.2.2]:

- Complete data (Day of hospitalization and discharge or death)
- Incomplete data (missing day of hospitalization or discharge/death)

The following table and figure provide descriptive statistics of the primary endpoint. The table and figures should impute values of 28 days for patients who died and should censor patients with missing discharge date at the time of last follow up.

- Figure: Kaplan-Meier plot of time to hospital discharge/death (only ITT and ITT age subgroups)
- Table: with the following estimates from the Kaplan-Meier curves- 25th, 50th and 75th percentile along with min and max values in hours [14.2.3.1.x]

- The between group difference in median time to discharge will be used to estimate the treatment effect and will be reported along with a 95% two-sided confidence interval.
- Additionally, data from median, min, max converted to “days, hours”
- The p-value for the 2 group comparison of the primary endpoint analysis will be performed using the Shaw-Fay method as described in appendix 1.
- Sensitivity analyzes to exam effect of missing death or discharge data. (only ITT and ITT age subgroups)
  - Figure with Kaplan-Meier curves and Shaw-Fay p-values on the ITT only where missing death or discharge dates are imputed in the placebo group as censored at the time of last follow up and in the experimental group are imputed as events at day 28.
  - Figure with Kaplan-Meier curves and Shaw-Fay p-values on the ITT only where missing death or discharge dates are imputed in both groups as events at day 28.
  - For any imbalance seen in baseline characteristics ( $p < .05$ ) perform a cox proportional hazards model with deaths receiving event times of 28 days. Missing discharge dates will be censored at last follow up time.

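### The SAP splits its formulation subgroups at 13 years although the protocol changes formulation at 12, and it leaves out the protocol's planned under-12 versus 12-and-over subgroup

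*SAP*

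**What the plan says.** The protocol uses 12 years wherever age determines product or analysis group.

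- Section 5.2 states: "The formulation for children younger than 12 years is the currently licensed suspension of nitazoxanide". Patients of 12 and over receive tablets. The footnote to Table 3 gives the same age limit for tablets.
- Section 5.1 uses the same age for the strata: "Randomization will be stratified by sites and by adult and pediatric (<12 years").
- Section 9.2 lists the subgroup analyses after the influenza-positive one: "Other subgroups include age (<12 years of age" against 12 and over), and pathogen type.

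The SAP, under Subject Populations, uses other ages. Its age subgroups are under 18 and 18 or over. Its formulation subgroups are 13 to under 18, described as "children that take the adult tablet formulation", and under 13, justified with "as this is the age for pediatric formulation". The formulation subgroups "may be omitted depending on the number of subjects enrolled in each pediatric subgroup".

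SAP section 11 applies these groups to the main outcome: "Primary Endpoint (ITT, ITT age subgroups, ITT pediatric formulation subgroups, ITT virology subgroups"). The baseline age bands in SAP section 3 also break at 13: "≥8 years to <13 years, ≥13 years to <18 year".

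**The concern.** There are two separate problems.

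The first is a label that does not match its contents. The SAP's stated reason for cutting at 13 is the formulation age, and the protocol puts that age at 12. A 12-year-old given tablets would be counted in the group reported as suspension. The products differ in more than form: Protocol 5.2 gives 200 mg per dose as suspension at ages 4 to 11, and two 300 mg extended-release tablets per dose from 12. A reader of the under-13 result would take it to describe suspension recipients only.

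The second is an omitted analysis, and it is the more substantial problem. The protocol's age subgroup matches a randomisation stratum, so it is the only age split on which allocation was stratified. The SAP carries forward the influenza and pathogen subgroups from Protocol 9.2 but replaces the age subgroup with a split at 18 and does not explain the change. If under 12 versus 12 and over is run only after unblinding, it will look post hoc although the protocol planned it.

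**Working it through.** The plan gives no figure to reproduce. The check compares the age cut-points and then sizes the effect.

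**Step 1. Formulation by age.** Protocol rule: suspension if age < 12, tablet if age ≥ 12. SAP label: pediatric formulation if age < 13, adult tablet if 13 ≤ age < 18.

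| Age (years) | Product, Protocol 5.2 | SAP formulation subgroup | Agree? |
|---|---|---|---|
| 1 to <12 | suspension | <13, pediatric formulation | yes |
| 12 to <13 | tablet | <13, pediatric formulation | no |
| 13 to <18 | tablet | 13 to <18, adult tablet | yes |

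The two rules disagree for exactly one year of age.

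**Step 2. Can the protocol's age subgroup be rebuilt from the SAP's groups?** The SAP's analysis groups cut at 13 and 18, and its baseline bands cut at 2, 8, 13, 18 and 65. None falls at 12, so no SAP group, alone or combined, gives under 12 versus 12 and over. Moving the formulation cut from 13 to 12 would not restore it. Those subgroups stop at 18, so they would compare under 12 with 12 to 17 rather than with everyone of 12 and over, and they are optional.

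**Step 3. Where the age groups are used.** The age subgroups at 18 also govern mortality (SAP section 7), laboratory values (section 10) and secondary endpoints (section 12). The formulation subgroups are named only in section 11. If they are dropped, no planned efficacy or safety summary separates suspension from tablet recipients.

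**Step 4. Size of the omitted split.** Protocol Table 2 has 253 patients aged 2 to <12 and 1,123 aged ≥ 12, of 1,376. Assuming the trial has the same mix:

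- under 12: 253/1,376 = 0.1839; 0.1839 × 290 = 53.3
- 12 and over: 1,123/1,376 = 0.8161; 0.8161 × 290 = 236.7

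Table 2 leaves out 1-year-olds, who are eligible, so the under-12 count is probably low.

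**Step 5. Size of the mislabelling.** The documents give no count of 12-year-olds. Assume 0.5% to 2% of 290:

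- low: 0.005 × 290 = 1.45
- high: 0.02 × 290 = 5.8

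Rough plausibility check, itself resting on assumptions: the 2-to-11 group fills at 53.3/10 = 5.3 patients per year of age, and the 12-and-over group at 236.7/69 = 3.4 if ages 12 to 80 were evenly filled. Both lie inside 1.45 to 5.8.

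Share of the SAP's under-13 group who are 12-year-olds on tablets:

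- low: 1.45/(53.3 + 1.45) = 2.6%
- high: 5.8/(53.3 + 5.8) = 9.8%

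Including 1-year-olds would enlarge the denominator and lower both shares. If ages 1 to 12 were filled evenly, the share would be 1/12 = 8.3%, within the range.

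**The case against.** The strongest counter-argument is that little is lost. The SAP's subgroups are defined by age, and within each one randomised nitazoxanide is compared with randomised placebo, so 12-year-olds in the under-13 group do not bias that comparison. The under-13 group contains every patient under 12 and consists mostly of them, so it approximates the younger half of the protocol's split. Age is recorded for each patient, so a cut at 12 can be produced at any time. The protocol lists age among its other subgroups, below the influenza-positive analysis, and the sample size does not rest on it. The share of 12-year-olds used above has no source in the documents.

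Much of this stands. The within-group comparison is valid, the mislabelling covers one year of age, and the percentages in Step 5 are illustrative. Recorded ages also mean that no data are lost.

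It does not remove the point. The SAP's own reason for the cut at 13 contradicts the protocol. An optional under-13 group with no group of 12 and over beside it does not replace a planned two-group comparison. Being able to run that comparison later is not the same as having it in the analysis plan before unblinding.

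**Conclusion.** The concern holds in both parts. The formulation subgroups are wrong as written against Protocol 5.2: one year of age falls in a group whose label contradicts the product received, about 1 to 6 patients of 290 under the assumed 0.5% to 2% share. The protocol's age subgroup, about 53 versus 237 patients if the Table 2 mix applies, is not specified in the SAP, and its replacement by a split at 18 is unexplained. That conclusion does not depend on the assumed share.

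The consequence is limited to subgroup and descriptive output. The split at 18 mislabels nobody, and the overall ITT comparison is untouched. This should be corrected before unblinding, but it does not threaten the trial's main conclusion.

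**What to change.** Before unblinding:

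1. Reconcile SAP Subject Populations with Protocol 5.2 on the formulation age, and define the formulation subgroups to match. On the protocol as it stands, that is under 12 (suspension) and 12 to under 18 (tablet).
2. Add under 12 versus 12 and over to SAP section 11 as the protocol-specified age subgroup for the primary endpoint. This is needed in addition to item 1.
3. Minor: put a break at 12 in the baseline age bands of SAP section 3, so that the table can describe that subgroup.
4. Minor: if the split at 18 is kept, label it as an additional analysis not specified in the protocol.

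The cost is SAP wording and table shells. Data collection, sample size, power and alpha do not change.
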